### Duration of Response (DOR)

Duration of response will be based on RECIST v1.1 as determined by BICR and calculated for confirmed responders of the ITT Analysis Set. The DOR will be measured from the time at which criteria are first met for CR or PR (whichever is first recorded) until the first date that recurrence or PD is objectively documented (taking as reference for PD the smallest measurements recorded on study).

DOR is only defined for subjects who have a confirmed BOR of CR or PR. Per the BOR definition, subjects with an overall response of CR or PR must have a repeat tumor assessment performed no less than 4 weeks after the criteria for response are first met. The first date at which a CR or PR response was noted will be used to calculate DOR, not the date of the confirmatory tumor assessment. Subjects who do not have PD or death will be censored at the date of their last disease assessment. For subjects who started a subsequent anti-cancer therapy before having a documented PD, the last disease assessment prior to the start of the

## Statistical Analysis Plan

Regeneron Pharmaceuticals Inc. / Protocol: CMP-001-010 IQVIA Biotech (Confidential) Project # RZA44091

subsequent therapy will be used. Details of the censoring rules are provided in Table 1a.

DOR will be calculated as follows:

DOR (months) = (Event/Censoring Date – Response Start Date + 1) / 30.4375

Progression-Free Survival (PFS)

Progression-free survival is defined as the time from first dose of study treatment to the date of documented PD based on RECIST v1.1 by BICR or death from any cause, whichever occurs first. Subjects who are alive and progression-free at the time of analyses will be censored in the analyses at the date of their last disease assessment. For subjects who started a subsequent anti-cancer therapy before having a documented PD, the overall response assessment evaluated after new anti-cancer treatment will not be considered for PFS calculation, and the last disease assessment prior to the start of the subsequent therapy will be used. Details of the censoring rules are provided in Table 1a.

PFS will be calculated as follows:

PFS (months) = (Event or Censoring Date – First Dose Date + 1) / 30.4375

All events of RECIST v1.1 disease progression or death will be counted regardless of whether the event occurred while the subject was on study drug or had previously discontinued treatment. Subjects who do not experience disease progression or death before the analysis cutoff date will be censored at the date of last adequate tumor assessment. Date of censoring for these subjects will be based on the last tumor assessment prior to missing the assessments. Censoring rules are summarized in Table 1a. If a subject meets the criteria for more than 1 censoring rule, PFS will be censored at the earliest censoring date.

Secondary Efficacy Assessments by Investigator

The secondary efficacy endpoints of ORR, BOR, DCR, DOR and PFS by investigator assessments will be derived using the same approach as above.

Overall Survival (OS)

Overall survival will be calculated as the time from first dose of study treatment to the date of death due to any cause. Subjects who are alive or lost to follow-up at the time of the analysis data cutoff will be censored at the time of last known alive date, or at data cutoff date, whichever occurs first. Censoring rules are detailed in Table 1c, and the last contact date will be derived as shown in Table 2.

OS will be calculated as follows:

OS (months) = (Death or Censoring Date – First Dose Date + 1) / 30.4375

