iPFS is defined as the time from date of first dose of study drug to date of iCPD per iRECIST as assessed by Investigator or death, whichever occurs first. Censoring rules are detailed in Table 1b.

Table 1a: Censoring Rules for the PFS/DOR

Situation	Outcome	Date	Event Description/ Censoring Reason
PD per RECIST v1.1 on/before new anticancer therapy or data cutoff date, whichever is earlier	Event	Earliest date of tumor assessment documenting PD	PD per RECIST v1.1
Death without PD per RECIST v1.1 and not receiving new anticancer therapy on/before data cutoff date	Event	Date of death	Death without PD per RECIST v1.1
[PFS only] Subjects with no post-baseline assessments	Censored	Date of First Dose of Study Drug	No Adequate Disease Assessment per RECIST v1.1
No PD per RECIST v1.1 or Death as of data cutoff date and subject not received new anticancer therapy or received it after the data cutoff date	Censored	Date of last disease assessment on/before data cutoff date	Alive without Documented PD
No PD per RECIST v1.1 or Death as of data cutoff date and new anticancer therapy started before the data cutoff date	Censored	Date of last disease assessment prior to new anticancer therapy	Subsequent Anti-cancer Therapy without Documented PD
PD per RECIST v1.1 or Death after new anticancer therapy and the new anticancer started before data cutoff date	Censored	Date of last disease assessment prior to new anticancer therapy	Documented PD or Death after Subsequent Anti-cancer Therapy
PD per RECIST v1.1 or Death after new anticancer therapy and the new anticancer started after data cutoff date	Censored	Date of last disease assessment on/before data cutoff date	Documented PD or Death after Subsequent Anti-cancer Therapy
PD per RECIST v1.1 or Death immediately following two or more consecutive disease assessments missed since the last adequate disease assessment	Censored	Date of last adequate tumor assessment prior to missing assessments	PD or Death after Missing >= 2 Consecutive Disease Assessments
Withdrew consent or lost to follow- up before PD per RECIST v1.1 or Death	Censored	Date of last adequate disease assessment	Discontinued from Study without Documented PD or Death

Regeneron Pharmaceuticals Inc. / Protocol: CMP-001-010 IQVIA Biotech (Confidential) Project # RZA44091

Table 1b: Censoring Rules for the iPFS/iDOR

Situation	Outcome	Date	Event Description/ Censoring Reason

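### A sentence in the SAP's PFS text censors event-free subjects before a gap in scans, while Table 1a censors them at their last scan; applied literally it lowers the PFS estimate relative to Table 1a.

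*SAP*

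**What the plan says.** The PFS part of SAP VIII.A deals with event-free subjects three times.

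- First paragraph: "Subjects who are alive and progression-free at the time of analyses will be censored in the analyses at the date of their last disease assessment".
- Second paragraph: "Subjects who do not experience disease progression or death before the analysis cutoff date will be censored at the date of last adequate tumor assessment".
- The sentence that follows: "Date of censoring for these subjects will be based on the last tumor assessment prior to missing the assessments". Its subject can only be the people just named, those without progression or death. It gives no threshold for how many scans must be missed.

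The second paragraph then points to Table 1a and closes with a tie rule: "If a subject meets the criteria for more than 1 censoring rule, PFS will be censored at the earliest censoring date".

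The Table 1a row for event-free subjects ("No PD per RECIST v1.1 or Death as of data cutoff date and subject not received new anticancer therapy", or therapy received only after the cutoff) has no missed-scan condition. Its date is "Date of last disease assessment on/before data cutoff date". The table's only row triggered by missed scans requires an event: "PD per RECIST v1.1 or Death immediately following two or more consecutive disease assessments missed since the last adequate disease assessment". That event is then censored at the last adequate assessment before the gap.

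Protocol 9.5.5 says only that subjects alive and progression-free are censored and that the SAP may add rules, so it does not settle the date.

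**The concern.** Censoring at the last scan before a gap is a usual way to handle an event that surfaces after a long unobserved interval, because its true date is uncertain. A subject who misses a scan, returns and is shown to be progression-free poses no such problem: the later scans establish the status across the gap. Dropping those scans discards valid follow-up.

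It also does so selectively. The same post-gap time is kept if the subject later progresses, so whether follow-up counts depends on the outcome. The later risk sets lose progression-free subjects and keep those who go on to progress, which raises the estimated hazard and lowers the Kaplan-Meier curve. The median and the landmark rates listed in SAP VIII.C (6, 9, 12 and 18 months, for example) are exposed. SAP VIII.A derives investigator-assessed PFS in the same way, so that analysis is exposed too.

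**Working it through.** The plan states no expected PFS and no missed-scan rate, so there is no PFS figure of its own to reproduce. The check has two parts: individual records, then the size on a Kaplan-Meier curve.

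**Individual records.** Inputs: scans at W13 and every 9 weeks (SAP II.A); PFS in months = (date − first dose date + 1) / 30.4375 (SAP VIII.A). Day 1 of week w is study day 7(w − 1) + 1.

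| Record | Table 1a | Sentence read literally |
|---|---|---|
| SD at W13 and W22, W31 missed, SD at W40, W49 and W58, no event | censored W58 | censored W22 |
| Same record, then PD at W67 | event W67 | event W67 |
| SD at W13 and W22, W31 missed, cutoff before the next scan | censored W22 | censored W22 |
| SD at W13 and W22, W31 and W40 missed, PD at W49 | censored W22 | censored W22 |

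First record:
- W58 is day 400, and 400 / 30.4375 = 13.1 months.
- W22 is day 148, and 148 / 30.4375 = 4.9 months.
- The loss is 252 days, or 36 weeks: 252 / 30.4375 = 8.3 months.

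The first two rows show the asymmetry. The last two show where there is none: scans missed only at the end, and an event straight after two or more misses. The bias therefore comes from gaps followed by at least one progression-free scan.

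**Size, first set of assumptions.** None of these inputs is in the documents except the scan schedule and Table 1a: 40,000 simulated subjects per scenario; PFS a 30/70 mixture of exponentials with medians of 18 and 3.5 months; scans missed independently; cutoff uniform from 5 to 20 months after first dose; events straight after two or more misses censored as in Table 1a.

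| Scans missed | 12-month PFS, Table 1a | 12-month PFS, literal | Loss (points) | Subjects affected |
|---|---|---|---|---|
| 5% | 27.4% | 24.9% | 2.5 | 4.5% (2.0 of 44) |
| 10% | 27.8% | 22.5% | 5.3 | 8.6% (3.8 of 44) |
| 15% | 28.8% | 20.7% | 8.1 | 11.9% (5.2 of 44) |

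The 44 is the enrolled number in SAP II.C. With 24 to 36 months of follow-up and the other inputs unchanged, the 12-month loss is about 1 to 3 points and the 18-month loss about 2 to 5. If the sentence needs two or more consecutive misses, the 12-month loss is about 1 point or less.

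**Size, second set of assumptions.** 30,000 subjects per scenario; exponential time to PD with median 4 or 8 months; 0% or 20% never progressing; 60-week accrual; cutoff 22 or 104 weeks after the last subject. Literal 12-month PFS was below the Table 1a value in all 24 scenarios:
- 5% missed: 0.1 to 3.6 points lower.
- 10% missed: 0.2 to 7.5 points lower.
- 20% missed: 0.4 to 15.5 points lower.

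One scenario (median 8 months, 20% never progressing, early cutoff, 10% missed) gives 50.7% under Table 1a, 43.2% literally, and 51.0% with no scans missed. The median was often unchanged because events fall on a 9-week grid; in some scenarios it dropped by one or two scan intervals (for example 13.1 to 11.0 months). Requiring two or more consecutive misses cut the 12-month loss to 0 to 2.2 points.

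**The case against.** The strongest reply is that the literal reading is not the intended one. The sentence speaks of assessments in the plural, and the only missed-scan situation the SAP defines is two or more in a row. It may be a displaced fragment of that Table 1a row, or it may mean the last scan before scanning stopped; the effect is then small or nil. The first PFS paragraph, Table 1a and the DOR and iDOR text all use the last disease assessment, and the PFS text refers to Table 1a twice. This stands as a reason to expect limited harm. It does not remove the conflict: the sentence names event-free subjects, states neither limit, and nothing in the SAP ranks table over text.

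Three stronger inferences are tempting and should not be drawn.

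- A reader might infer that the earliest-date rule resolves the conflict in favour of the pre-gap date. That rule directly follows the reference to Table 1a, so it can equally be read as choosing among the table's rows.
- A reader might take the 18-month contrast as the headline. With 15% of scans missed and the short cutoff, the first simulation gives 17.9% under Table 1a and 7.1% literally. Under those inputs only about 0.3 of 44 subjects would be at risk at 18 months (about 5 at 12 months), so it describes nothing this trial could estimate.
- A reader might infer that the reported PFS will be wrong, or that two programmers will certainly differ. The documents show only that they could.

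The short cutoff suits the ad-hoc analysis (SAP VI.G). The SAP also serves the study report (SAP I.A), with treatment of up to two years (SAP II.F), where the loss is smaller.

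**Conclusion.** The contradiction is real and lies within the SAP. For event-free subjects with a gap followed by progression-free scans, the sentence and Table 1a give different dates, and the sentence makes censoring depend on outcome. The direction, downward relative to Table 1a, follows from the rule itself. It is not a claim about distance from the true curve: missed scans also delay detection of progression, which pushes PFS up and can offset part of the effect.

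The size is conditional. The 12-month range of about 3 to 8 points (short follow-up) or 1 to 3 points (24 to 36 months) rests on 5% to 15% of scans missed at random and on the assumed PFS mixture. On the narrower readings of the sentence it is about 1 point or less, or nil.

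PFS is a secondary endpoint, and the SAP makes all analyses descriptive and exploratory (SAP II.C), so no test or decision rule changes. With no test, the estimates are themselves the result, and a rule that could move 2 to 5 of 44 subjects is worth settling.

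**What to change.** 1. Delete the sentence on missed assessments from the second PFS paragraph, or limit it to the Table 1a row for progression or death straight after two or more consecutive missed assessments.
2. Give one rule for event-free subjects in both text and table: censor at the last adequate assessment on or before the data cutoff and before any new anticancer therapy. Define adequate as evaluable by the assessor of that analysis, BICR or Investigator, since both PFS analyses share the derivation.
3. State that Table 1a governs PFS censoring and that the earliest-date rule applies among its rows.

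The cost is SAP wording and a check of the PFS derivation program. No new data are needed. If the sentence has already been programmed literally, a few censoring dates move later.

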### Statistical Analysis Plan

Regeneron Pharmaceuticals Inc. / Protocol: CMP-001-010 IQVIA Biotech (Confidential) Project # RZA44091

Immune Objective Response Rate (iORR)

iORR is defined as the proportion of subjects with an immune best overall response (iBOR) of confirmed immune complete response (iCR) or confirmed immune partial response (iPR) based on immunotherapy Response Evaluation Criteria in Solid Tumors (iRECIST) by Investigator assessment.

Subjects who continue study treatment beyond PD per RECIST v1.1 will be assessed by the Investigator according to iRECIST. Subjects with an iCR or iPR per iRECIST must have a confirmatory assessment performed at least 4 weeks after the initial assessment where response was declared by the Investigator and all scans should be performed at least 2 weeks after the previous CMP-001 IT injection to prevent injection-related pseudoprogression.

The confirmed iORR will be calculated as the number of subjects with a confirmed iCR or iPR divided by the number of subjects in the analysis population [iORR = (confirmed iCR + confirmed iPR)/number of subjects]. The two-sided 95% Clopper-Pearson CIs will be calculated for the iORR.

The immune best overall response (iBOR) will be derived as below: iCR > iPR > iSD > iCPD > iUPD > NE

If assessments are not performed or cannot be assessed following iUPD, and there is no subsequent iCPD, iSD, iPR or iCR, iUPD will be continue be used and the subject will be censored at the date of iUPD.

*Immune Duration of Response (iDOR).* 

iDOR is defined as the time from the date of the first immune response (iCR or iPR) to the date of immune confirmed progressive disease (iCPD) by Investigator assessment.

iDOR is only defined for Subjects who have a confirmed iBOR of iCR or iPR. Subjects with a response of iCR or iPR must have a repeat tumor assessment performed no less than 4 weeks after the criteria for response are first met. The first date at which an iCR or iPR response was noted will be used to calculate iDOR, not the date of the confirmatory tumor assessment. Subjects who did not have iCPD or death will be censored at the date of their last disease assessment. Censoring rules are detailed in Table 1b.

*Immune Progression-Free Survival (iPFS).* 

Regeneron Pharmaceuticals Inc. / Protocol: CMP-001-010 IQVIA Biotech (Confidential) Project # RZA44091

iPFS is defined as the time from date of first dose of study drug to date of iCPD per iRECIST as assessed by Investigator or death, whichever occurs first. Censoring rules are detailed in Table 1b.

Table 1a: Censoring Rules for the PFS/DOR

Situation	Outcome	Date	Event Description/ Censoring Reason
PD per RECIST v1.1 on/before new anticancer therapy or data cutoff date, whichever is earlier	Event	Earliest date of tumor assessment documenting PD	PD per RECIST v1.1
Death without PD per RECIST v1.1 and not receiving new anticancer therapy on/before data cutoff date	Event	Date of death	Death without PD per RECIST v1.1
[PFS only] Subjects with no post-baseline assessments	Censored	Date of First Dose of Study Drug	No Adequate Disease Assessment per RECIST v1.1
No PD per RECIST v1.1 or Death as of data cutoff date and subject not received new anticancer therapy or received it after the data cutoff date	Censored	Date of last disease assessment on/before data cutoff date	Alive without Documented PD
No PD per RECIST v1.1 or Death as of data cutoff date and new anticancer therapy started before the data cutoff date	Censored	Date of last disease assessment prior to new anticancer therapy	Subsequent Anti-cancer Therapy without Documented PD
PD per RECIST v1.1 or Death after new anticancer therapy and the new anticancer started before data cutoff date	Censored	Date of last disease assessment prior to new anticancer therapy	Documented PD or Death after Subsequent Anti-cancer Therapy
PD per RECIST v1.1 or Death after new anticancer therapy and the new anticancer started after data cutoff date	Censored	Date of last disease assessment on/before data cutoff date	Documented PD or Death after Subsequent Anti-cancer Therapy
PD per RECIST v1.1 or Death immediately following two or more consecutive disease assessments missed since the last adequate disease assessment	Censored	Date of last adequate tumor assessment prior to missing assessments	PD or Death after Missing >= 2 Consecutive Disease Assessments
Withdrew consent or lost to follow- up before PD per RECIST v1.1 or Death	Censored	Date of last adequate disease assessment	Discontinued from Study without Documented PD or Death

Regeneron Pharmaceuticals Inc. / Protocol: CMP-001-010 IQVIA Biotech (Confidential) Project # RZA44091

Table 1b: Censoring Rules for the iPFS/iDOR

Situation	Outcome	Date	Event Description/ Censoring Reason
iCPD per iRECIST between scheduled disease assessments on/before new anticancer therapy or data cutoff date, whichever is earlier	Event	Earliest date of tumor assessment documenting iUPD	iCPD per iRECIST
Death without iCPD per iRECIST and not receiving new anticancer therapy on/before data cutoff date	Event	Date of death	Death without iCPD per iRECIST
[iPFS only] iUPD per iRECIST at the time of PD per RECIST v1.1, continued study treatment without further tumor assessments as of data cutoff date	Censored	Date of the last tumor assessment on/before data cutoff date	No Adequate Disease Assessment per iRECIST
iUPD per iRECIST, continued study treatment with subsequent disease assessments but no confirmed PD (i.e., iCPD not assigned) or Death as of data cutoff date and subject not received new anticancer therapy or received it after the data cutoff date	Censored	Date of the last tumor assessment as of data cutoff date	Alive without Documented iCPD
iUPD per iRECIST, continued study treatment, but started a new anti-cancer therapy before data cutoff date without evidence of iCPD or Death	Censored	Date of the last tumor assessment prior to new anti-cancer therapy	Subsequent Anti-cancer Therapy without Documented iCPD
iCPD per iRECIST or Death after new anticancer therapy and the new anticancer started before data cutoff date	Censored	Date of last disease assessment prior to new anticancer therapy	iCPD or Death after Subsequent Anti-cancer Therapy
iCPD per iRECIST or Death after new anticancer therapy and the new anticancer started after data cutoff date	Censored	Date of last disease assessment on/before data cutoff date	iCPD or Death after Subsequent Anti-cancer Therapy
iUPD per iRECIST, continued study treatment, iCPD or Death immediately following two or more consecutive disease assessments since the last adequate disease assessment	Censored	Date of last adequate tumor assessment prior to the first missed assessment	iCPD or Death after Missing >= 2 Consecutive Disease Assessments
Withdrew consent or lost to follow-up before iCPD per iRECIST or death	Censored	Date of last adequate disease assessment	Discontinued from Study without Documented iCPD or Death

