- a. EOT assessments to be performed within 7 days following subject discontinuation from study treatment. Removal of a subject from CMP-001 treatment is defined as the time at which the Investigator decides to discontinue study treatment. If a subject has CMP-001 withheld for more than 3 consecutive doses for any reason during the Q3W dosing period, resumption of treatment must be discussed with the Medical Monitor, otherwise, the subject will be discontinued from study treatment and will have all EOT assessments performed.
- b. The 100DFU is a safety follow-up visit that may be conducted at the study site or via phone. This visit should occur 100 days (+7) after the EOT. NOTE: If a subject's 100DFU, PTFU, and LTSFU visits overlap, then the visits can be combined into 1 study site visit.
- c. Posttreatment follow-up will be conducted Q3mo (± 2 weeks) for all subjects who discontinue study treatment for reasons other than disease progression (either per RECIST v1.1, iRECIST, or clinical PD per Investigator) but have not met criteria for study discontinuation. These subjects should remain on study and receive disease assessments Q3mo, until discontinuation.
- d. LTSFU will be conducted Q3mo (\pm 4 weeks) after the EOT visit or the last disease assessment date in PTFU and may occur via phone.
- e. CMP-001 dosing will begin on W1D1. Weekly dosing: A window of ± 2 days is permitted for CMP-001 dosing from W1D1 to W7D1. The first dose of CMP-001 may be administered SC or IT, at the discretion of the Investigator; all subsequent doses are planned to be administered IT until no injectable lesions remain. Subjects must complete all 7 weekly CMP-001 doses before moving to the Q3W dosing schedule. Q3W dosing (W10D1+): A window of ±3 days is permitted for CMP-001 dosing from W10D1 throughout the study. When nivolumab is permanently discontinued due to an immune related AE, CMP-001 must also be permanently discontinued. Refer to Section 5.3 for Treatment Compliance.
- f. Nivolumab dosing will begin on W1D1 and continue Q3W throughout the study. When CMP-001 injection and nivolumab dosing fall on the same day, CMP-001 injection will be given before nivolumab dosing. Refer to Section 5.1.1 for Nivolumab Dosing.

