7.2.4.1. Disease Assessment Beyond Progressive Disease

Subjects with PD per RECIST v1.1 as determined by Investigator assessment who are clinically stable should remain on treatment and have a follow-up scan performed at least 4 weeks after the initial date of PD to confirm progression per RECIST v1.1. Subjects who receive study treatment beyond PD per RECIST v1.1 will have subsequent disease assessments evaluated using iRECIST by the Investigator. Disease assessments should continue according to the Schedule of Assessments (Table 1).

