7.8. Posttreatment Follow-up

Subjects who discontinue study treatment and transition into PTFU will continue to have assessments collected per the time points specified in the Schedule of Assessments (Table 1).

VV-RIM-00381493-1.0 Approved - 27 Nov 2024 GMT-5:00

Posttreatment follow-up disease assessments will continue until disease progression, initiation of another cancer treatment, death, loss to follow-up, withdrawal of consent, or End of Clinical Trial.

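### Immune PFS does not count the progression that ended treatment as an event on its own date, because no scheduled scan can confirm it and Table 1b has no row for these subjects

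*SAP*

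**What the plan says.** **Endpoint.** SAP VIII.A defines iPFS as "time from date of first dose of study drug to date of iCPD per iRECIST as assessed by Investigator or death". An unconfirmed progression is not an event. Once confirmed, Table 1b dates the event back to "Earliest date of tumor assessment documenting iUPD".

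**No later assessment.** In the iORR paragraph of SAP VIII.A, after the best-response hierarchy, a sentence covers iUPD with no subsequent evaluable assessment: "iUPD will be continue be used and the subject will be censored at the date of iUPD".

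**Table 1b.** All four iUPD rows require that study treatment continued, for example "iUPD per iRECIST, continued study treatment, but started a new anti-cancer therapy before data cutoff date without evidence of iCPD or Death". The death row does not: "Death without iCPD per iRECIST and not receiving new anticancer therapy on/before data cutoff date" is an event at the date of death. The rows for iCPD or death after new therapy, and for withdrawal or loss to follow-up, do not depend on continued treatment either.

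**Imaging after progression.** Protocol 4.5 lists RECIST v1.1 progression as a reason to stop and leaves continuation to the Investigator. Under Protocol 7.2.4.1, clinically stable subjects "should remain on treatment and have a follow-up scan performed at least 4 weeks after the initial date of PD to confirm progression". Those who stop have an end-of-treatment (EOT) assessment within 7 days (Table 1, footnote a). Posttreatment imaging is "for all subjects who discontinue study treatment for reasons other than disease progression" (footnote c; Section 4.5 agrees). Section 7.8 adds: "Posttreatment follow-up disease assessments will continue until disease progression, initiation of another cancer treatment". Long-term follow-up may be by telephone (footnote d).

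**The concern.** Two subjects with the same progression on the same scan are treated differently according to whether the Investigator continued treatment. If treatment continues and a later scan confirms, the event falls on the date of the first scan. If treatment stops for that progression, the subject is censored on that date or becomes an event only at a later death.

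The censoring is likely to be informative. Section 7.2.4.1 keeps clinically stable subjects on treatment, so those who stop at once probably have the worse outlook. Kaplan-Meier assumes that censored subjects have the same outlook as those who remain at risk.

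iPFS is a named secondary endpoint, and SAP VIII.C reports it with a median, landmark rates and confidence intervals. A reader who sees iPFS exceed RECIST v1.1 PFS would take the gap as benefit beyond progression, when part of it would come from this rule. The same applies to iDOR when the iUPD follows a confirmed iCR or iPR.

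**Working it through.** The documents give no iPFS figure, so there is none to reproduce.

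**1. Can EOT confirm the progression?** On-treatment scans may be taken up to 7 days before the visit (Table 1, footnote u), and EOT is within 7 days of stopping. If treatment stops at the visit the scan was taken for, EOT falls at most about 7 + 7 = 14 days after the progression scan, below the 28-day minimum. No later scan is scheduled. Section 7.2.1 asks for unscheduled scans to be collected; these could confirm some cases, but none is required.

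**2. Direction.**
- iORR-paragraph rule: changing an event to censoring on the same date leaves every risk set unchanged and removes one event, so the Kaplan-Meier curve cannot fall at any time.
- Death row: the event moves to a later date, so the underlying event-time distribution shifts upward. Up to the first such death the curve cannot be lower. After it, heavy intervening censoring in a small sample could produce a large late step, so the upward direction there is systematic rather than guaranteed in every data set.

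**3. Illustration at Week 13.** From SAP II.C: 44 subjects. Assumed: all 44 at risk at Week 13, 28 with progression at that scan, a share *s* of these stopping, and 80% of continuers later confirmed and dated back to Week 13.

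- As written: 1 − 28(1 − s)(0.8)/44
- Stoppers would confirm at the same 80%: 1 − 28(0.8)/44 = 1 − 22.4/44 = 49.1%, whatever *s* is
- All stoppers count as events: 1 − [28(1 − s)(0.8) + 28s]/44

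| s | As written | Same 80% | All stoppers count |
|---|---|---|---|
| 25% | 1 − 16.8/44 = 61.8% | 49.1% | 1 − 23.8/44 = 45.9% |
| 50% | 1 − 11.2/44 = 74.5% | 49.1% | 1 − 25.2/44 = 42.7% |
| 75% | 1 − 5.6/44 = 87.3% | 49.1% | 1 − 26.6/44 = 39.5% |

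The excess is 28s(0.8)/44 against the first comparator (13, 25 and 38 points) and 28s/44 against the second (16, 32 and 48 points). The median is not reached at Week 13 as written; under either comparator it is reached by then. The death row does not alter these Week 13 values, because those deaths come later.

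**4. Does the death row remove the bias later on?** A simulation with 200,000 subjects per scenario assumed scans at Week 13 and every 9 weeks, a 24-month cutoff, a median of 9 months from progression to death, and 30% to 60% of subjects starting new therapy. The reference counts every progression at its scan. Results are 12-month iPFS:

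| Latent median PFS | Share stopping | Reference | Censor at iUPD | With death row |
|---|---|---|---|---|
| 3 months | 25% | 8% | 17% | 18% |
| 3 months | 50% | 8% | 33% | 30–31% |
| 3 months | 75% | 8% | 59% | 43–47% |
| 5 months | 25% | 22% | 33% | 32–33% |
| 5 months | 50% | 22% | 49% | 44–46% |
| 5 months | 75% | 22% | 71% | 57–61% |

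Counting deaths reduces the excess at higher stopping shares but does not remove it.

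**The case against.** **There is a visit after stopping.** A reader might infer that these subjects are never imaged again. The documents do not support that: EOT includes a disease assessment and unscheduled scans are collected. What is missing is a scheduled scan at four weeks or more. Protocol 3.1 and SAP II.A also keep posttreatment subjects in follow-up, and Protocol 4.6 does not list progression as a reason to leave the study. Both refer to the Schedule of Assessments, however, and its footnote c excludes those who stopped for progression.

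**Other rules apply.** A reader might infer that the censoring sentence is the only rule that fits, so that every such subject ends as a non-event. That is too strong. The death, withdrawal and post-new-therapy rows do not require continued treatment, and the iDOR paragraph has its own rule of censoring at the last assessment. None of them makes the progression an event on its own date.

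**The sentence may not reach these subjects.** It sits under iORR, and SAP II.A and VIII.A describe iRECIST evaluation for subjects who continue beyond progression, so a stopper may have no iUPD recorded. This stands as an ambiguity. Against it, censoring has no meaning for a response rate, Protocol 7.2 has the Investigator apply iRECIST to all disease assessments, and efficacy uses the ITT set. Limiting iPFS to continuers would be a selection that the SAP would have to state.

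**Limited consequence.** All analyses are descriptive, in 44 subjects. iPFS is Investigator-assessed and absent from the ad-hoc list (SAP VI.G). Reasons for censoring will be tabulated, and some difference from PFS is inherent in requiring confirmation. This limits the weight of the point but does not remove the bias.

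**Conclusion.** The point holds in this form: for subjects who stop because of a first RECIST progression, the SAP has no Table 1b iUPD row, its two applicable rules conflict when the subject dies, and under either rule iPFS is biased upward. iDOR is affected in the same way after a confirmed iCR or iPR.

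The direction follows from the rules; the size does not. The share stopping at first progression, the number progressing at Week 13 and the confirmation rate are all assumptions. On those used, Week 13 iPFS is overstated by 13 to 38 points if stoppers would confirm as often as continuers, and by 16 to 48 points if all stoppers count. The second comparison assumes that no stopper has pseudoprogression. Protocol 1.1 cites 24 of 327 subjects (7%) with progression not later confirmed. That denominator is not subjects with progression, so it suggests, without establishing, that such cases are few.

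A reader might extend this to the main efficacy results. The documents do not support that: ORR does not use the rule, and Table 1a counts the same progression as a PFS event. The SAP should be corrected before iPFS is analysed, but the primary result does not depend on it.

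**What to change.** 1. Reconcile the censoring sentence in the iORR paragraph with Table 1b, so that one rule applies to iPFS and iDOR.
2. Add a Table 1b row: iUPD, study treatment discontinued because of disease progression (RECIST v1.1, iRECIST or clinical), and no later assessment showing iSD, iPR or iCR = event at the iUPD date. Apply it to iPFS, and to iDOR when the iUPD follows a confirmed iCR or iPR.
3. Give this row precedence over the death row, and over censoring for new anticancer therapy, withdrawal or loss to follow-up that occurs after that iUPD.
4. Leave subjects who stop for other reasons, such as toxicity or withdrawn consent, and those still on treatment awaiting a scan, under the existing censoring rules.
5. State that iPFS is derived for all ITT subjects, with progression at stopping treated as iUPD, in line with Protocol 7.2.
6. Keep the current rule as a sensitivity analysis, and report how many events are confirmed iCPD and how many are unconfirmed iUPD with stopping for progression.

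The cost is one sentence, one table row and a short derivation note, with no new data and no change to visits or treatment. iPFS becomes less favourable, and any pseudoprogression among those who stop counts as an event; items 4 and 6 limit and expose that.
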